4.2.3.3 Handling of Dropouts and Missing Data

Missing data will not be imputed and only observed values will be reported in the summary tables and listings. Treatment discontinuation visit will be mapped according to Section 3.3.2.

4.2.3.4 Primary Analysis of Primary Endpoint

Laboratory data will be summarized based on the Safety Analysis Set. Summaries of the individual values and change from baseline will be presented by treatment group and visit according to the principles outlined in section 3.3.1. The number and proportion of patients with liver enzyme abnormalities and reduced platelet counts will be summarized by treatment group and visit, including a summary of the maximum (for AST, ALT and TBL) or minimum value (for platelet count) recorded post-baseline.

The composite measure of the PFC index and corresponding ratio of AZD8233 to placebo will be presented by treatment group and visit. Box plots over time will be produced by treatment group for the composite measure and for the fold-change of the six individual biomarkers. A spaghetti plot over time of the fold-change of the six individual biomarkers will also be produced for each subject.

Shift tables will be presented for select laboratory parameters (clinical chemistry and hematology). Spaghetti plots over time will be produced for ALT, AST, TBIL and gamma GPT, with the corresponding reference range overlaid on top.

Clinical laboratory data will be reported in standard international units.

4.2.4 Primary Endpoint – Vital Signs, ECG and Cardiac Telemetry

4.2.4.1 Definition

Vital Signs

The vital sign measurements to be summarized are:

- Systolic blood pressure (mmHg)
- Diastolic blood pressure (mmHg)
- Pulse rate (bpm)
- Body temperature (oral) (°C).

ECG

The following parameters or time intervals will be recorded for each ECG: RR, PR interval, QRS duration, QT interval, QTcF interval, and ECG mean heart rate (HR). The Investigator will judge whether the overall interpretation is ‘normal’ or ‘abnormal’.

Cardiac Telemetry

Cardiac telemetry results will be reviewed by the Investigator and clinically important results are stored.

4.2.4.2 Derivations

Vital sign measurements, ECG and cardiac telemetry results will be assigned to analysis visits as described in Section 3.3.2.

Change from baseline for vital sign measurements and ECG parameters (where applicable) will be calculated for all post-baseline visits as the respective visit value minus the baseline value.

Vital Signs

Based on the respective reference range indicators, the following flags will be applied to all vital sign measurements; ‘Normal’ (if the value is within the normal reference range), ‘Low’ (if the value is below the normal reference range) or ‘High’ (if the value is above the normal reference range).

Parameter	Normal Reference Ranges
Systolic blood pressure	80 - 140 mmHg
Diastolic blood pressure	50 - 90 mmHg
Heart rate	50 - 100 bpm
Temperature	<=37°C

ECG

Outlier categories with respect to QTcF will be defined as follows:

- Absolute value > 450 ms and \leq 480 ms
- Absolute value > 480 ms and \leq 500 ms
- Absolute value > 500 ms
- Increase from baseline > 30 ms and \leq 60 ms
- Increase from baseline > 60 ms

4.2.4.3 Handling of Dropouts and Missing Data

Missing data will not be imputed and only observed values will be reported in the summary tables and listings. Treatment discontinuation visit will be mapped according to Section 3.3.2.

4.2.4.4 Primary Analysis of Primary Endpoint

Vital Signs

Vital signs will be summarized based on the Safety Analysis Set. Summaries of the individual values and change from baseline will be presented by treatment group and visit according to the principles outlined in section 3.3.1.

ECG

ECG parameters will be summarized based on the Safety Analysis Set. Summaries of the individual values and change from baseline will be presented by treatment group and visit according to the principles outlined in section 3.3.1. Outliers with respect to QTcF will be tabulated using the categories defined in Section 4.2.4.2.

Cardiac Telemetry

Results for 12-lead ECG real-time cardiac telemetry will be listed based on the Safety Analysis Set including the overall assessment, specifics of abnormalities and the start and stop date/time.

4.2.5 Secondary Endpoint - Pharmacokinetics

4.2.5.1 Definition

Where possible, the following PK parameters will be determined.

AUC	Area under the plasma concentration-time curve from time zero extrapolated to infinity. AUC is estimated by $AUC(0\text{-last}) + \frac{C_{last}}{\lambda_z}$ where C_{last} is the last observed quantifiable concentration.
$AUC_{(0\text{-last})}$	Area under the plasma concentration-curve from time zero to the time of last quantifiable analyte concentration.
$AUC_{(0\text{-}24)}$	Area under the concentration-time curve from time zero to 24 hours post-dose.
$AUC_{(0\text{-}48)}$	Area under the concentration-time curve from time zero to 48 hours post-dose.
$AUC\tau$	Area under the plasma concentration-time curve during the dosing interval
CL/F	Apparent total body clearance of drug from plasma after extravascular administration.
C_{max}	Maximum observed plasma concentration.
C_{trough}	Observed trough plasma concentration
λ_z	Terminal rate constant, estimated by log-linear least-squares regression of the terminal part of the concentration-time curve.
MRT	Mean residence time of the unchanged drug in the systemic circulation.

RAC (AUC)	Accumulation ratio based on AUC
RAC (C _{max})	Accumulation ratio based on C _{max}
t _{1/2z}	Half-life associated with the terminal slope (λz) of a semi-logarithmic concentration-time curve
t _{lag}	Time delay between drug administration and the first observed concentration in plasma
t _{last}	Time of last quantifiable concentration.
t _{max}	Time to reach peak or maximum observed concentration following drug
Vz/F	Apparent volume of distribution during the terminal phase after extravascular administration.

The following PK parameters will be determined, where possible, from urine concentrations.

Ae _(t1-t2)	Amount of analyte excreted unchanged in urine from time t1 to t2
fe _(t1-t2)	Percentage of analyte excreted unchanged in urine from t1 to t2
Ae _(0-last)	Cumulative amount of analyte excreted at the last sampling interval
fe _(0-last)	Cumulative percentage of dose excreted unchanged into the urine from time zero to the last measured time point for an analyte, estimated by dividing Ae(0-last) by dose
CLR	Renal clearance of drug from plasma, estimated by dividing Ae(0-24) by AUC(0-24)

Additional PK parameters may be determined where appropriate.

4.2.5.2 Derivations

The geometric mean is calculated as the exponential of the arithmetic mean calculated from the data on the natural log scale.

The percent coefficient of variation is calculated as: $CV (\%) = \sqrt{(\exp(s^2) - 1)}$ where s is the standard deviation of the data on a log scale.

Handling of values below the lower limit of quantification (BLQ)

Plasma concentrations below the limit of quantification (BLQ) from the time of pre dose sampling (t = 0) up to the time of the first quantifiable concentration will be set to a value of 0. After the first quantifiable concentration, BLQ plasma concentrations will be set to missing for the calculation of PK parameters unless it is considered to be a true characteristic of the profile of the drug.

If two or more consecutive BLQ concentrations are followed by quantifiable concentrations in the terminal portion of the concentration curve, the profile will be deemed to have terminated and therefore these quantifiable values will be set to missing for the calculation

of the PK parameters unless there is a scientific rationale not to do so, which will be documented in the CSR.

Any embedded BLQ value (between two quantifiable concentrations) will be set to missing for the PK analysis.

If an entire concentration-time profile is BLQ, the profile is excluded from the PK analysis.

For descriptive statistics plasma concentrations that are below the LLOQ will be handled as follows:

- At a time point where less than or equal to 50% of the values are BLQ, all BLQ values will be set to LLOQ, and all descriptive statistics will be calculated.
- At a time point where more than half of the values are BLQ, the mean, SD, geometric mean and CV% will be set to Not Determined (ND). The max value will be reported from the individual data, and the min and median will be set to BLQ.
- If all values are BLQ at a time point, no descriptive statistics will be calculated for that time point. Not applicable (NA) will be written in the field for SD and CV% and BLQ will be written in fields for mean, geometric mean, min, median, and max.
- The number of BLQ values (n below LLOQ) will be reported for each time point.
- Where there is no result, these will be set to missing.

Urine concentrations that are below the LLOQ will be handled as follows:

- BLQ values should be set to zero for the calculation of individual Ae.
- Any resulting Ae values equal to zero should be set to missing for the calculation of the summary statistics.

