Blood sampling for other lipid parameters	X ^m	X ^m	X ^m (pre-dose and then 48 h post-dose)	X ^{m, n} (pre-dose)	X ^{m, n}		X ^m (pre-dose and then 24 h post-dose)		X ^m	X ^m

Table 1 Schedule of Activities (Part A)

Visit Number	Screening	Treatment Period					Follow-up Period			Corre-sponding Section in Protocol
		1	2	3, 6	4, 5, 7, 8	9	Telephone contact ^k	10 to 16	17 (Final Follow-up Visit/ ED Visit)	
Study Day/Week	Days -28 to -4	Day -1	Days 1 to 3	Days 8 ^a , 29	Days 15, 22, 36, 44	Day 56	Days 57 to 59	Day 64	Weeks 2, 4, 6, 8, 10, 12, 14 (after last dose)	Week 16 (after last dose)
Visit Window	-	-	-	± 1 day	± 1 day	± 1 day		+2 days	± 2 days	± 2 days
Exploratory biomarker sampling										
Plasma and urine samples to be stored in the Biobank until further analysis ⁱ			X (pre-dose)	X (pre-dose)			X (pre-dose)		X (Weeks 2 and 4 after last dose)	X
Pharmacokinetics										
Plasma for AZD8233 and total full length ASOs of AZD8233 ^j			X (pre-dose and then 0.5, 1, 1.5, 2, 2.5, 3, 4, 5, 6, 8, 10, 12, 24, 36 and 48 h post dose)	X (pre-dose)	X		X (pre-dose and then 0.5, 1, 1.5, 2, 2.5, 3, 4, 5, 6, 8, 10, 12, 24, 36 and 48 h post dose)		X	X

Table 1 Schedule of Activities (Part A)

Visit Number	Screening	Treatment Period					Follow-up Period			Corre-sponding Section in Protocol
	1	2	3, 6	4, 5, 7, 8	9	Telephone contact ^k	10 to 16	17 (Final Follow-up Visit/ ED Visit)		
Study Day/Week	Days -28 to -4	Day -1	Days 1 to 3	Days 8 ^a , 29	Days 15, 22, 36, 44	Day 56	Days 57 to 59	Day 64	Weeks 2, 4, 6, 8, 10, 12, 14 (after last dose)	Week 16 (after last dose)
Visit Window	-	-	-	± 1 day	± 1 day	± 1 day		+2 days	± 2 days	± 2 days
Urine for total full length ASOs of AZD8233			X (pre-dose and intervals 0-6, 6-12, 12-24 h post-dose)				X (pre-dose and intervals 0-6, 6-12, 12-24 h post-dose)			Section 8.5.1

ASO: Antisense oligonucleotides; BMI = body mass index; ET = early termination; FSH = follicle-stimulating hormone; hs-CRP = high sensitive C-reactive protein; IMP: Investigational medicinal product; LDL-C = low-density lipoprotein cholesterol; LH = luteinizing hormone; PCSK9 = proprotein convertase subtilisin/kexin type-9; SAE: Serious adverse event

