4.2.5.4 Primary Analysis of Secondary Endpoint

A listing of PK blood sample collection times as well as derived sampling time deviations will be provided. A listing of urine sample collection start and stop times will be provided. Urine amount and fraction of dose excreted (by interval and cumulative) will be listed.

Pharmacokinetic Concentrations

Plasma concentrations, amount excreted in urine (Ae), and fraction of dose excreted (per collection interval and cumulative) and PK parameters will be summarized by analytes and timepoints using descriptive statistic, number of non-missing observations, n below LLOQ, arithmetic mean, SD, geometric mean, geometric coefficient of variation (CV%), min, median, max and based upon the PK analysis set.

Where the actual time that a sample was taken deviates by more than the specified time allowances from the nominal time then concentration will be excluded from the summary statistics and statistical analysis.

Nominal Time	Time allowance
Pre-dose	Up to 30 minutes prior to dosing
0.5 h post dose	± 2 minutes
1 h post dose	± 5 minutes
1.5 h post dose	± 5 minutes
2 h post dose	± 5 minutes
2.5 h post dose	± 5 minutes
3 h post dose	± 10 minutes
4 h post dose	± 10 minutes
5 h post dose	± 10 minutes
6 h post dose	± 10 minutes
8 h post dose	± 10 minutes
10 h post dose	± 30 minutes
12 h post dose	± 30 minutes
24 h post dose	± 1 hour
36 h post dose	± 1 hour
48 h post dose	± 1 hour

Data from subjects excluded from the PK population will be included in the data listings, but not in the summaries or in the inferential statistics.

For t_{max} and time of last quantifiable plasma concentration (t_{last}) only n, median, minimum and maximum will be used.

Pharmacokinetic parameters will be rounded for reporting purposes in the summary tables and subject listings, as per the PK order form provided by AZ.

Individual plasma concentrations versus actual time will be plotted in linear and semi-logarithmic scale, with separate plots for each subject. Plots will be based on the PK analysis set.

Combined individual plasma concentration versus actual times will be plotted in linear and semilogarithmic scale. Plots will be grouped by dose level and based on the PK analysis.

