If the sample at the end of the profile is missing on Day 57 the concentration may be set equal to the pre-dose value for the calculation of AUC τ assuming linear PK and steady state conditions apply.

If a plasma or urine concentration value is considered anomalous due to being inconsistent with the expected pharmaceutical profile it may be appropriate to exclude this data point from the PK analysis. However, the exclusion of any data must have strong justification and will be documented in the study report. Embedded BLQs may be considered anomalous depending on the characteristics of the drug.

Urine PK parameters will be calculated based on measurements with the ECL assay. In case of an incomplete urine collection in any of the specified collection intervals (eg, spilled sample), the calculation of the fraction of dose excreted into urine as well as renal clearance will be subject to discretion of the AZ study pharmacokineticist.

The amount excreted in urine (Ae) will be calculated using a urine density of 1.0 g/mL. Urine concentrations below LLOQ will be treated as numerical zero.

The amount of analyte excreted into the urine from time t1 to t2 [Ae(t1-t2)] and percentage excreted unchanged in urine from t1 to t2 [fe(t1-t2)] will be calculated by collection interval and cumulatively for all collection intervals.

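### Parts A and C: setting zero urinary amounts to missing makes per-interval Ae summaries describe only participants with quantifiable excretion

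*SAP*

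**What the plan says.** The wording is the same in the Part A and Part C SAPs.

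- **Individual amounts (4.2.5.2):** "BLQ values should be set to zero for the calculation of individual Ae". Section 4.2.5.4 repeats this for urine: "Urine concentrations below LLOQ will be treated as numerical zero".
- **Summaries (4.2.5.2):** "Any resulting Ae values equal to zero should be set to missing for the calculation of the summary statistics".
- **Statistics reported (4.2.5.4):** Ae and the fraction of dose excreted (fe) are summarised per collection interval and cumulatively with "number of non-missing observations, n below LLOQ, arithmetic mean, SD, geometric mean", then geometric CV%, minimum, median and maximum. Individual amounts and fractions are also listed.
- **Geometric mean (4.2.5.2):** "The geometric mean is calculated as the exponential of the arithmetic mean calculated from the data on the natural log scale".
- **Plasma, for comparison (4.2.5.2):** "At a time point where less than or equal to 50% of the values are BLQ, all BLQ values will be set to LLOQ". When more than half are BLQ, the mean, SD, geometric mean and CV% are reported as Not Determined. Urine has no such threshold.
- **Urine sampling (Protocol 1.3, Tables 1 and 3):** "pre-dose and intervals 0-6, 6-12, 12-24 h post-dose", around the Day 1 and Day 57 doses.

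**The concern.** A urine sample below the limit is informative, because it usually marks one of the lowest excreters in that interval. Deleting the resulting zero turns a mean over all treated participants into a mean over those with measurable drug, and the minimum becomes the smallest positive value. The log-scale statistics need positive values. The arithmetic mean, SD, median, minimum and maximum do not.

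Ae is a listed secondary PK parameter in both parts, with about 8 participants on active drug, so one deleted value matters. With no threshold for urine, the tabulated mean could in the extreme be one person's value. At stake is how well a descriptive PK table represents renal excretion in an interval. No hypothesis test depends on it.

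**Working it through.** **Inputs.** Active participants per part: n = 8 (Protocol 9.2). The zero rule, the statistics and the intervals are as set out above. The documents give no urine LLOQ, no BLQ rate and no urine result, so there is no plan figure to reproduce. Anything beyond step 1 rests on stated assumptions.

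**Step 1: deleted against kept.** Let k of 8 participants have zero Ae in an interval, and let m be the mean of the rest.

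- Reported mean = m
- Mean with zeros kept = (8-k)m/8
- Ratio = 8/(8-k)

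**Step 2: against the true mean.** A BLQ amount is not exactly zero. It lies between 0 and the LLOQ amount L (LLOQ concentration times urine volume, taken here as equal across participants). The true mean then lies between (8-k)m/8 and [(8-k)m + kL]/8. For k=1 and m = 3L, the upper limit is (21 + 1)L/8 = 2.75L, and 3/2.75 = 1.09.

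| k | Reported ÷ zeros kept | Excess over true mean if m = 3L |
|---|---|---|
| 1 | 8/7 = 1.14 | +9% to +14% |
| 2 | 8/6 = 1.33 | +20% to +33% |
| 3 | 8/5 = 1.60 | +33% to +60% |
| 4 | 8/4 = 2.00 | +50% to +100% |

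With m = 1.5L the ranges are +4% to +14% (k=1) and +20% to +100% (k=4). With m = 10L they are +13% to +14% and +82% to +100%. At k=7 the reported mean is one person's value, 8 times the mean with zeros kept.

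**Step 3: which error is larger.** Let b be the mean true amount of the BLQ participants (0 ≤ b < L). Deleting zeros overstates the mean by k(m-b)/8. Keeping them understates it by kb/8, which is less than kL/8. Deletion has the larger error whenever m > 2b, and m ≥ 2L is enough to guarantee that.

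**Step 4: simulation.** Lognormal amounts over three intervals were simulated with 400,000 draws per scenario. Medians and variability were assumed.

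| BLQ in the interval | Zeros deleted ÷ true mean | Zeros kept ÷ true mean |
|---|---|---|
| 8% | 1.06 | 0.97 |
| 22% | 1.22 | 0.95 |
| 50% | 1.38 to 1.63 | 0.69 to 0.82 |

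**Step 5: cumulative Ae.** Cumulative Ae over 0-24 h is zero, and so dropped, only if all three intervals are BLQ. Otherwise each BLQ interval contributes 0 and lowers the total. In the same simulation, reported ÷ true was:

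- 0.97 to 0.98 when mainly the later intervals were BLQ
- 0.85 to 1.01 at intermediate levels
- 0.88 to 1.30 when about half the participants had every interval BLQ
- 1.15 to 1.72 when 73% to 90% did

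**Step 6: fe and CLR.** Section 4.2.5.1 derives cumulative fe as Ae(0-last) over dose, and CLR as Ae(0-24) over AUC(0-24). Both come from individual Ae, where the zero is retained. The deletion rule names Ae only, and nothing is said about zero fe. If fe zeros are kept, mean fe will not equal mean Ae over dose, and the two differ by the factor in step 1.

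**The case against.** Much of the opposing case stands.

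- **Conditional.** With no zero Ae the rule does nothing. A reader might assume that BLQ is common in the later intervals, but no document gives a rate.
- **Cumulative excretion.** A reader might infer that mean urinary excretion is overstated throughout. Step 5 shows that the cumulative figure can be too low.
- **No contradiction.** A reader might see zero in one sentence and missing in the next as inconsistent. The two sentences govern different stages, individual calculation and summary. The numerical-zero statement sits with the calculation of Ae and agrees with the first.
- **fe and CLR.** A reader might infer that these are inflated too. As written, a rule on Ae summaries changes no individual fe or CLR. What remains is that the treatment of zero fe in summaries is unstated.
- **Disclosure.** The number of observations, the number below LLOQ and individual listings are already planned, so exclusions can be seen.
- **The alternative is also biased.** Zeros understate the mean, noticeably so once half the values are BLQ.

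On the other side, disclosure lets a reader detect the exclusion but does not correct the tabulated mean, median or minimum. Keeping zeros has an error bounded by the LLOQ amount, whereas the error from deletion grows with the amounts excreted by the others. The same section already has a threshold rule for plasma.

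**Conclusion.** The point holds for per-interval Ae in Parts A and C and is minor. Where k of 8 active participants have zero Ae, the arithmetic mean is 8/(8-k) times the mean with zeros kept. That is 1.14 for one zero and 2.0 for four. Against the true mean the excess is somewhat smaller: +9% to +14% and +50% to +100% respectively, if quantifiable amounts average three times the LLOQ amount. The SD, median and minimum likewise describe quantifiable excreters only.

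This rests on zeros occurring, on 8 evaluable active participants, and on BLQ participants having excreted less on average than the others. The documents do not support a general upward bias in cumulative Ae, fe or CLR. The endpoint is secondary and descriptive, and no stated decision depends on it.

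**What to change.** In section 4.2.5.2 of both SAPs, replace the zero-to-missing sentence with a rule that:

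1. keeps zeros in n, arithmetic mean, SD, median, minimum and maximum of Ae;
2. gives the geometric mean and CV% for positive values only, with their own n;
3. applies the same handling to fe;
4. reports the mean, SD, geometric mean and CV% as Not Determined when more than 50% of values in an interval are BLQ, as for plasma.

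The number below LLOQ is already planned and needs no change.

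The cost is a sentence or two per SAP and a small programming change, with no new data. The downside is that keeping zeros understates the arithmetic mean, by less than kL/8 (less than the LLOQ amount for each BLQ participant, spread over 8). Item 4 withholds the mean where that would matter most. The Part A SAP is already a post-database-lock edition, so a supplementary row or footnote in the CSR is enough there.

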4.2.5.3 Handling of Dropouts and Missing Data

Not applicable

4.2.5.4 Primary Analysis of Secondary Endpoint

A listing of PK blood sample collection times as well as derived sampling time deviations will be provided. A listing of urine sample collection start and stop times will be provided. Urine amount and fraction of dose excreted (by interval and cumulative) will be listed.

Pharmacokinetic Concentrations

Plasma concentrations, amount excreted in urine (Ae), and fraction of dose excreted (per collection interval and cumulative) and PK parameters will be summarized by analytes and timepoints using descriptive statistic, number of non-missing observations, n below LLOQ, arithmetic mean, SD, geometric mean, geometric coefficient of variation (CV%), min, median, max and based upon the PK analysis set.

Where the actual time that a sample was taken deviates by more than the specified time allowances from the nominal time then concentration will be excluded from the summary statistics and statistical analysis.

Nominal Time	Time allowance
Pre-dose	Up to 30 minutes prior to dosing
0.5 h post dose	± 2 minutes
1 h post dose	± 5 minutes
1.5 h post dose	± 5 minutes
2 h post dose	± 5 minutes
2.5 h post dose	± 5 minutes
3 h post dose	± 10 minutes
4 h post dose	± 10 minutes
5 h post dose	± 10 minutes
6 h post dose	± 10 minutes
8 h post dose	± 10 minutes
10 h post dose	± 30 minutes
12 h post dose	± 30 minutes
24 h post dose	± 1 hour
36 h post dose	± 1 hour
48 h post dose	± 1 hour

Data from subjects excluded from the PK population will be included in the data listings, but not in the summaries or in the inferential statistics.

For t_{max} and time of last quantifiable plasma concentration (t_{last}) only n, median, minimum and maximum will be used.

Pharmacokinetic parameters will be rounded for reporting purposes in the summary tables and subject listings, as per the PK order form provided by AZ.

Individual plasma concentrations versus actual time will be plotted in linear and semi-logarithmic scale, with separate plots for each subject. Plots will be based on the PK analysis set.

Combined individual plasma concentration versus actual times will be plotted in linear and semilogarithmic scale. Plots will be grouped by dose level and based on the PK analysis.

Figures for the arithmetic mean concentration-time data will be presented for all groups (pool data from all treatment groups and for placebo) overlaid on the same plot, in both a linear and semi-logarithmic scale (SD on the linear scale and gSD on the semi-logarithmic scale).

Additional graphical presentations of PK data may be added at the discretion of the PK scientist.

Pharmacokinetic data will be presented by analytes and timepoints. A listing of all concentration-time data will be presented by dose level.

The following rules will be followed with regards to the number of decimal places and presentation of data in the tables and listings of concentration data:

1. Source data shall be used in all derived PK concentrations without prior rounding.
2. The mean, standard deviation (SD), geometric mean and median will be tabulated to one more significant digit compared to the source data, but with a maximum of four significant digits.
3. Minimum and maximum values will be tabulated to the same precision as the source data, but with a maximum of four significant digits.
4. Geometric coefficient of variation (CV) % and coefficient of variation (CV%) will be presented to one decimal place.

Graphical Presentation

For individual figures, concentrations that are BLQ will be regarded as missing, with the exception of pre-dose BLQ values which will be set to zero for linear scale plots.

For mean plots, BLQ values will be handled as described for the summary tabulations so that the same plasma concentration values are used in the mean data graphs as those given in the descriptive statistics summary table for each time point. All mean plots will be based on the PK analysis set.

Pharmacokinetic Parameters

Pharmacokinetic parameters will be derived using noncompartmental methods with WinNonlin® Professional Version 6.4, or higher, (Certara) and/or SAS® Version 9.3, or higher (SAS Institute, Inc., Cary, North Carolina). All descriptive and inferential statistical computations will be performed using SAS® Version 9.3, or higher.

The actual sampling times, recorded in the raw data, will be used in the final plasma PK parameter calculations. If actual times are missing, nominal times may be used.

Nominal sampling times will be used for interim plasma PK parameter calculations.

Nominal times will be used for the calculation of urine PK parameters.

Concentration data will be used as supplied by the analytical laboratory for PK analysis. The units of concentration and resulting PK parameters, with amount and concentration units, will be presented as they are received from the analytical laboratory.

Dose normalized parameters for AUC_{last} , AUC and C_{max} will be calculated by dividing the original parameter by dose.

The C_{max} and time to reach peak or maximum observed concentration or response following drug administration (t_{max}) will be derived directly from the plasma concentration-time profiles. For multiple peaks the highest post dose concentration will be reported as C_{max} . In the case that the multiple peaks are of equal magnitude, the earliest t_{max} will be reported.

Terminal elimination half-life, estimated as $(\ln 2)/\lambda_z$, where λ_z refers to the terminal elimination rate constant, will be estimated by log linear least squares regression of the terminal part of the concentration-time curve.

The choice of data points used to estimate λ_z should follow the general guidelines:

- If there is more than 1 phase, use only observations from the terminal phase.
- In general, the minimum data requirements are 3 measured concentrations spanning three half-lives. Where $t_{1/2}$ is estimated over less than three half-lives, the values will be flagged in the data listings.
- Should include the last measurable concentration.
- Include only observations after C_{max} .
- The adjusted correlation coefficient (regression coefficient adjusted for λ_z , N, goodness of fit statistic for calculation of λ_z ; R^2 adj) should be ≥ 0.80 .

Area under the plasma concentration-curve will be calculated using trapezoidal methods when concentration is increasing and logarithmic trapezoidal method when concentrations are decreasing (linear up log down).

Three concentrations higher than the lower limit of quantification (LLOQ) are required as a minimum for the AUC parameter to be calculated.

If the pre-dose concentration prior to the first dose is missing it will be set to zero by default. If the pre-dose sample on Day 57 is missing it may be set equal to the concentration at the end of the dosing interval for the calculation of area under the plasma concentration-time curve in the dosing interval (AUC τ) assuming linear PK and steady state conditions apply.

If the sample at the end of the profile is missing on Day 57 the concentration may be set equal to the pre-dose value for the calculation of AUC τ assuming linear PK and steady state conditions apply.

If a plasma or urine concentration value is considered anomalous due to being inconsistent with the expected pharmaceutical profile it may be appropriate to exclude this data point from the PK analysis. However, the exclusion of any data must have strong justification and will be documented in the study report. Embedded BLQs may be considered anomalous depending on the characteristics of the drug.

Urine PK parameters will be calculated based on measurements with the ECL assay. In case of an incomplete urine collection in any of the specified collection intervals (eg, spilled sample), the calculation of the fraction of dose excreted into urine as well as renal clearance will be subject to discretion of the AZ study pharmacokineticist.

The amount excreted in urine (Ae) will be calculated using a urine density of 1.0 g/mL. Urine concentrations below LLOQ will be treated as numerical zero.

The amount of analyte excreted into the urine from time t1 to t2 [Ae(t1-t2)] and percentage excreted unchanged in urine from t1 to t2 [fe(t1-t2)] will be calculated by collection interval and cumulatively for all collection intervals.

